## 1 Background and rationale

## 1.1 Purpose of the health economic analysis plan

The purpose of this health economic analysis plan (HEAP) is to describe the analysis and reporting procedure intended for the economic analyses to be undertaken. The analysis plan is designed to ensure that there is no conflict with the protocol and associated statistical analysis plan (SAP) and it should be read in conjunction with them. This HEAP largely follows the guidance as suggested by Thorn et al. This document has been written based on information contained in the trial protocol version 2.0, dated 22 May 2023 and SAP version 1.0, dated 14 May 2024.

## 1.2 Background

Ankle fracture is one of the most common fractures of the lower limb. Based on a 1988-2012 analysis of UK primary care records, the annual incidence of ankle fracture amongst adults aged 50 years and above (104 per 100,000 personyears) was estimated to be greater than amongst adults aged 49 years and below (75 per 100,000 person-years).

Treatments for ankle fractures range from conservative plaster casts or boots to surgical fixation. Physiotherapy after surgery or a period of immobilisation in a cast or boot aims to reduce pain, enhance mobility, and improve balance and coordination as well as muscle strength. Many adults aged 50 years and above experience loss of confidence and fear of future injuries after ankle fracture. There is good evidence that progressive exercise reduces risk of falls and improves mobility in other clinical populations, so a tailored progressive exercise intervention supervised by a physiotherapist could have the potential to improve recovery in this group, especially where rehabilitation needs are often more complex. However, there is insufficient evidence regarding physiotherapist-supervised rehabilitation after ankle fracture, especially, for adults aged 50 years and above.

## 1.3 Aims and objectives

The aim of this trial is to evaluate the clinical and cost-effectiveness of physiotherapist-supervised versus self-directed rehabilitation in improving ankle function for people aged 50 years and over with ankle fractures.

The primary objective of this trial is to quantify and draw inferences on differences in ankle function at 6 months post-randomization between the trial intervention groups (supervised vs self-directed rehabilitation).

The secondary objectives of this trial include:

- ankle function at 2 and 4 months
- ankle pain at 2, 4 and 6 months
- health-related quality of life (HRQoL) at 2, 4 and 6 months
- physical function at 4 and 6 months
- self-efficacy to exercise at 4 and 6 months
- exercise adherence at 4 and 6 months
- risk of related complications over the initial 6 months
- cost-effectiveness of the interventions

#### 2 Trial design

AFTER is a multi-centre, parallel-group, superiority individually randomised controlled trial assessing the clinical effectiveness of supervised versus self-directed rehabilitation in improving ankle function for people aged 50 years and over after ankle fracture. The trial will be conducted at secondary care trauma departments in a minimum of 20 NHS hospitals and their related physiotherapy services.

Supervised and self-directed rehabilitation are defined as follows:

**Self-directed rehabilitation.** Self-directed rehabilitation is the provision of a standardised high-quality detailed advice on self-management and a set of exercises that can be progressed independently by the participant. The advice materials will be provided by a surgeon, nurse or physiotherapist during the fracture clinic appointment and will be accessible in both paper and online format. The online format comes with additional instruction videos.

**Supervised rehabilitation.** Participants referred to a physiotherapist will have four to six one-to-one sessions with a trial-trained physiotherapist, spread over three months from the initial session. This period allows sufficient time for neuromuscular adaptation to exercise. The first session will take place as soon as possible after the referral, and no later than three weeks from randomization. These sessions will be delivered via face-to-face or telephone/videoconference, depending on the usual mode of physiotherapy delivery for the participant. Physiotherapists will support participants with a highly structure but individualised progressive exercise programme focusing on recovery of movement, muscle strength, balance and gait training, and issue the exercise programme workbook. The programme uses contemporary evidence-based guidelines on exercise volume and load to optimise the physiological response.

For both forms of rehabilitation, commonly used simple methods to support exercise adherence such as goal setting and provision of an exercise diary will be used.

## 2.1 Inclusion criteria

Adults aged 50 years and over with an ankle fracture undergoing surgical fixation or non-surgical management and are provided with a cast or orthotic boot (non-removable or removable for non-weight bearing ankle movement) for at least four weeks were included.

## 2.2 Exclusion criteria

Participants will be excluded if they are deemed unable to adhere to trial procedures or complete questionnaires; were not ambulatory before the injury; or had contraindications to participation in an exercise programme.

#### 3 Economic approach

## 3.1 Aims and objectives

The primary objective of the health economic evaluation is to estimate the within-trial cost-effectiveness of supervised versus self-directed rehabilitation among patients with ankle fracture.

## 3.2 Overview of economic analysis

A within-trial economic analysis will be performed using individual participant-level data from AFTER. The analytical approaches will take the form of cost-utility analysis. Based on trial evidence, incremental cost-effectiveness ratios

(ICERs) will be calculated by taking a ratio of the difference in the mean costs and mean quality-adjusted life years (QALYs). Participants will primarily be recruited from secondary care trauma departments in a minimum of 20 NHS hospitals. The economic analysis will be from the NHS and personal social services (PSS) perspective and will compare the costs and consequences of each treatment group over six months after randomization.

#### 4 Data collection and management

## 4.1 Measurement of resource use

The therapist hours per treatment group will be computed from the frequency and duration of supervised and selfdirected rehabilitation sessions that will be captured via the Rehabilitation Initial Provision Log and the Treatment Log for supervised rehabilitation.

Inpatient care will be recorded in the form of treatment due to complications, which will be captured via the participant-reported Complications case report form (CRF) and verified by sites.

Resource use data will be collected using trial questionnaires given to participants at two- and six-months post-randomization. Participants will be required to note the frequency of their use of outpatient care, emergency department care, community health care, private care, social care, residential/nursing home care, informal care, and painkillers related to their ankle fracture or its treatment. Participants will also have their use of walking aids and time off work recorded.

#### 4.2 Valuation of resource use

All resource use will be valued in monetary terms using the latest and most appropriate UK unit costs or participant valuations estimated at the time of analysis. Adjustments will be made for inflation using the latest NHS hospital & community health services pay & prices index from the Personal Social Services Research Unit (PSSRU) Unit Costs compendium where applicable.

NHS reference costs will be employed to value hospital resource use (e.g. inpatient visits, emergency department visits and outpatient attendances) while the latest PSSRU Unit Costs of Health and Social Care will be used to value the therapist hours based on their grade per treatment group and community health and social services resource use. Unit cost of medications will be obtained from the Prescription Cost Analysis. The gender-specific median wage, obtained from the Office for National Statistics, will be used in the computation of the valuation of time taken off work by the participants due to the ankle fracture. The unit cost of the exercise diary and exercise programme workbook will be obtained from the trial team at its production cost.

## 4.3 Measurement of health outcomes

The primary health outcome measure will be QALYs derived from utility scores, obtained using the EQ-5D-5L HRQoL instrument. The EQ-5D-5L instrument facilitates the generation of a utility score from a person's health related quality of life. A utility score refers to the preference that individuals have for any particular set of health outcomes. The EQ-5D-5L's descriptive system consists of five health dimensions (mobility, self-care, usual activity, pain/discomfort, and anxiety/depression) each with five levels of severity to choose from (no problems, slight problems, moderate problems, severe problems, and extreme problems). Although not used to derive utilities, the

EQ-5D-5L HRQoL instrument also contains a visual analogue scale that records the participant's self-rated health from the worst to best health that they can imagine having. Measurement of HRQoL will be recorded using the trial questionnaires at baseline and at two-, four- and six-months post randomization.

#### 4.4 Valuation of health outcomes

Utility scores will be derived from responses to the EQ-5D-5L descriptive system. UK utility values will be derived using the approach recommended by NICE, which is currently recommending the validated mapping function onto the existing EQ-5D-3L A1 tariff set developed by the Decision Support Unit. QALYs will be calculated as the area under the baseline-adjusted utility curve of EQ-5D-3L utility scores using the trapezoidal rule.

#### 4.5 Data cleaning

Face validity tests will be conducted on data (e.g. to identify misspelt text) and checked against the source documents. Records of resource use across different time-points will also be cross-checked to ensure that there is no duplication. Corrections made will be documented in the statistical code.

## 4.6 Missing data

Before carrying out the within trial analysis, the trial data will be checked for any missing data. Where possible, the reasons for missing data will be ascertained, using the methodology described by Faria et al, and reported. The nature and pattern of 'missingness' will be carefully considered; in particular, whether data can be treated as missing at random (MAR) and multiple imputation methods may be used if the data is MAR.

## 5 Data analysis

The data analysis will be conducted once all participants have been followed for six months after randomization; no interim analysis will be undertaken. The data analysis will include a within-trial analysis using imputed data that will include all randomised participants, which is in accordance with the "intention to treat" (ITT) principle, taking a sixmonths' time horizon.

There will be no discounting of costs and benefits as the follow-up period is less than one year. Utilisation of resource use items will be summarised by trial allocation group and follow-up period and differences between groups will be analysed using t-tests for continuous variables and Pearson chi-squared ( $\chi^2$ ) test for categorical variables. Means and standard errors for values of each cost category will be estimated by treatment allocation and follow-up period. Mean differences in costs and QALYs between the treatment groups will be estimated using t-tests and the bootstrap 95% confidence interval that will be computed based on 10,000 replications. This bootstrap will use Monte Carlo simulations to resample many datasets based on the original data.

Cost and QALY data will be combined to calculate incremental cost-effectiveness ratios (ICERs) and net monetary benefit (NMB) statistics from the NHS and PSS perspective in the primary economic analysis. The primary economic analysis will use incremental cost-effectiveness thresholds of £20,000 and £30,000 per QALY as recommended by NICE. An additional £15,000 per QALY cost-effectiveness threshold will also be included to reflect recent trends in healthcare decision-making.

All analyses will be carried out using appropriate analytical software such as R or STATA. The relevant package and version number will be recorded in the health economics report.

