## 5.1 Uncertainty analysis

A nonparametric bootstrapping approach will be used to determine the level of sampling uncertainty surrounding the mean ICER by generating 10,000 estimates of incremental costs and benefits. Decision uncertainty characterised by estimating the probability that an option is cost-effective at different cost-effectiveness thresholds will be explored using cost-effectiveness acceptability curves (CEACs).

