## 5.2 Sensitivity analysis

Several sensitivity analyses will be undertaken to explore uncertainties surrounding key parameters in the economic evaluation as described in the following. First, the study perspective will be extended to a societal perspective which includes indirect costs (e.g. valuation of time off work). Second, complete case analysis will be used to assess the impact of missing data on the cost-effectiveness outcomes.

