#### 3.2 Randomization and Blinding

The randomization will be on a 1:1 basis to supervised versus self-directed rehabilitation, using a validated computer randomization program managed through a secure (encrypted) web-based service by the Oxford Clinical Trials Research Unit (OCTRU). Randomization will use a minimisation algorithm to ensure balanced allocation across the two treatment groups, stratified by centre and initial fracture management (surgical vs non-surgical). The first few participants will be randomised by simple randomization to seed the minimisation algorithm and a probabilistic element introduced to the algorithm to ensure the unpredictability of intervention allocation.

Full details of the randomization are available in AFTER\_RandomizationAndBlindingPlan\_V1.0\_27Jul2022, stored in the confidential statistical section of the Trial Master File (TMF).

Due to the nature of the intervention, it is not possible to blind participants or those delivering the intervention. The local research team at recruiting centres will also not be blinded to the treatment allocation.

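### The economic plan promises baseline-adjusted QALYs without saying how, then compares QALYs and costs with t-tests that take no covariate

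*SAP*

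**What the plan says.** HEAP 4.4 derives the outcome: "QALYs will be calculated as the area under the baseline-adjusted utility curve of EQ-5D-3L utility scores using the trapezoidal rule". It does not say what baseline-adjusted means, and no formula follows. The utilities come from four visits (HEAP 4.3): "Measurement of HRQoL will be recorded using the trial questionnaires at baseline and at two-, four- and six-months post randomization".

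HEAP 5 then names the estimator: "Mean differences in costs and QALYs between the treatment groups will be estimated using t-tests and the bootstrap 95% confidence interval". No covariate is mentioned. The ICER and net monetary benefit are built from these cost and QALY data.

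HEAP 5.1 handles uncertainty: "A nonparametric bootstrapping approach will be used to determine the level of sampling uncertainty surrounding the mean ICER by generating 10,000 estimates". No covariate is named there either. HEAP 5.2 lists two sensitivity analyses, "First, the study perspective will be extended to a societal perspective which includes indirect costs" and "Second, complete case analysis will be used to assess the impact of missing data on the cost-effectiveness outcomes", and neither is covariate-adjusted. Fracture management appears in the economic plan only as a subgroup (HEAP 5.3), and centre does not enter the economic comparison.

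SAP 3.2 makes centre and initial fracture management the minimisation factors. SAP 6.2.2 analyses the EQ-5D-5L utility score with a mixed model that adjusts for baseline utility, centre, fracture management, age and sex.

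**The concern.** HEAP 4.4 promises an adjustment, and HEAP 5 names an estimator that cannot make one. Nothing connects the two. An analyst could compute a plain area under the curve, or subtract each participant's baseline from the curve first, and claim to follow the plan either way. The two choices move the result in opposite directions when the arms differ at baseline, so the choice should not stay open once the data are visible.

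The ICER, net monetary benefit and acceptability curves all rest on these increments. The clinical EQ-5D result and the QALY result could also differ merely because one is adjusted and the other is not, although HEAP 1.1 says the economic plan is meant to avoid conflict with the SAP.

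For costs the point is smaller. The baseline-utility argument concerns QALYs, so only the omission of the minimisation factors applies to costs.

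**Working it through.** **Arm size.** The documents give no figure for the economic comparison, so the trial size is used only to fix the arm size. SAP 3.3 has a difference of 8, SD 21, 90% power and 5% two-sided significance. A t-based calculation gives 145.8, hence 146 per arm and 292 in total. Then 292/0.85 = 343.5, hence 344, or 172 per arm. The plan's figures reproduce. HEAP 5 includes all randomised participants through imputation, so 172 per arm is used below.

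**Assumptions not in the documents.** Utility SD 0.20 to 0.30, the same at each visit; equal correlation ρ of 0.3 to 0.7 between any two visits.

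**Weights.** For visits at 0, 2, 4 and 6 months the trapezoidal rule gives 1/12, 1/6, 1/6 and 1/12 year, which sum to 0.5.

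**Size of a chance imbalance.** One standard error of the baseline difference is SD × √(2/172). For SD 0.25 this is 0.25 × 0.1078 = 0.0270. Over SD 0.20 to 0.30 it is 0.022 to 0.032.

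**How much enters the QALY difference.** The expected shift is the imbalance times the slope of the QALY on baseline utility.

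- Plain area: slope = 1/12 + ρ × 5/12. At ρ = 0.5 this is 0.292, and 0.0270 × 0.292 = 0.0079 QALY, or £157 at £20,000 and £236 at £30,000 per QALY.
- Baseline subtracted: the baseline weight becomes 1/12 − 1/2 = −5/12, so slope = −(5/12)(1 − ρ). At ρ = 0.5 this is −0.208, and the shift is −0.0056 QALY, or −£112 at £20,000.
- Regression on baseline utility: the expected shift is zero when the relation is linear.

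**Standard error of the QALY difference.** Each is √(2/172) times the SD of the quantity compared.

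- Plain area: variance = SD² × [0.0694 + ρ × (0.25 − 0.0694)], where 0.0694 is the sum of squared weights.
- Baseline subtracted: variance = SD² × (1 − ρ) × 0.2361, where 0.2361 is the sum of squared weights and the weights sum to zero.
- Regression: the plain-area SE times √(1 − r²), where r is the correlation of the QALY with baseline utility (0.59, 0.73 and 0.85 at ρ = 0.3, 0.5 and 0.7).

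Results for SD 0.25; shifts are for a one-SE imbalance, in QALYs, with £ at 20,000 per QALY:

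| ρ | Plain area: shift | Plain area: SE | Subtracted: shift | Subtracted: SE | Regression: SE |
|---|---|---|---|---|---|
| 0.3 | +0.0056 (£112) | 0.0095 | −0.0079 (−£157) | 0.0110 | 0.0076 |
| 0.5 | +0.0079 (£157) | 0.0108 | −0.0056 (−£112) | 0.0093 | 0.0074 |
| 0.7 | +0.0101 (£202) | 0.0119 | −0.0034 (−£67) | 0.0072 | 0.0063 |

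Relative to regression, the plain-area SE is 24%, 46% and 88% larger at ρ = 0.3, 0.5 and 0.7. The subtracted SE is 44%, 26% and 13% larger. These ratios do not depend on the SD.

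**Full range.** Plain area runs from 0.0045 (SD 0.20, ρ 0.3) to 0.0121 (SD 0.30, ρ 0.7): £90 to £243 at £20,000 and £135 to £364 at £30,000. Subtraction runs, in the opposite direction, from 0.0027 (SD 0.20, ρ 0.7) to 0.0094 (SD 0.30, ρ 0.3): £54 to £189 at £20,000 and £81 to £283 at £30,000.

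**The case against.** The strongest reply is that HEAP 4.4 does state a baseline adjustment, at the derivation step and before any test. A reader might infer from HEAP 5 alone that the plan leaves baseline utility wholly unadjusted. The document does not establish that: what it shows is a promised adjustment with no method and an estimator that cannot supply one. This part of the reply stands, and it means that neither the sign nor the exact size of the shift can be read off the plan. It does not rescue the t-test. Subtracting baseline over-corrects, because later utilities correlate only partly with baseline, so an imbalance still enters with its sign reversed.

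The second reply is that under 1:1 randomisation the unadjusted difference is unbiased, and its interval already allows for chance imbalance. In the middle case the plain-area shift of 0.0079 is smaller than the SE of 0.0108. This also stands. A reader might call the analysis biased or invalid, and that goes too far. The harm is error conditional on the imbalance actually observed, with wider intervals and less decisive acceptability curves than the data allow.

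Third, leaving out centre and fracture management does not bias the mean difference. It costs precision and tends to make the t-test interval conservative.

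A reader might also set the monetary shift against the cost of a number of physiotherapy sessions. The documents give no unit cost for a session, so that comparison has no support.

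**Conclusion.** The point holds as a failure of specification with a real cost in precision. HEAP 4.4 and HEAP 5 are not reconciled, and on either reading of 4.4 a t-test lets a chance baseline imbalance into the QALY difference. Which reading applies decides the direction of the shift. In both cases the SE exceeds what regression on already planned data would give. All the monetary and SE figures rest on the assumed SD, the equal-correlation structure and 172 per arm, so they illustrate scale and are not predictions. The change should be made before the economic data are analysed.

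**What to change.** - **HEAP 4.4:** define the QALY as the plain trapezoidal area, and state that baseline adjustment is made in the comparison model.
- **HEAP 5:** replace the t-tests for incremental costs and QALYs with regression. Regress QALYs on arm, baseline utility and the minimisation factors, and costs on arm and the minimisation factors. Add age and sex to both to match the SAP. Seemingly unrelated regression is one suitable form. Centre is better as a random effect: with at least 20 hospitals, centre indicators can fail when a small centre drops out of a resample.
- **HEAP 5.1:** refit the model in each bootstrap replicate on paired cost and QALY data, state how the bootstrap is combined with the imputation, and derive the ICER, net monetary benefit and acceptability curves from the adjusted increments.
- Keep t-tests for the descriptive resource-use tables.

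The cost is a change of wording in the HEAP and slightly more programming. Baseline utility is already collected, and the SAP already uses the other covariates.

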## 5.1 Uncertainty analysis

A nonparametric bootstrapping approach will be used to determine the level of sampling uncertainty surrounding the mean ICER by generating 10,000 estimates of incremental costs and benefits. Decision uncertainty characterised by estimating the probability that an option is cost-effective at different cost-effectiveness thresholds will be explored using cost-effectiveness acceptability curves (CEACs).

## 5.2 Sensitivity analysis

Several sensitivity analyses will be undertaken to explore uncertainties surrounding key parameters in the economic evaluation as described in the following. First, the study perspective will be extended to a societal perspective which includes indirect costs (e.g. valuation of time off work). Second, complete case analysis will be used to assess the impact of missing data on the cost-effectiveness outcomes.

